5.5. Populations of participants for analysis

The following populations will be formed for analysis: ITT, PP and safety; additionally: ITT_NV, PP_NV, ITT_NV_BE, PP_NV_BE.

Statistical data analysis will be carried out in the following populations of participants:

1. Population of all included and randomized participants (intention-to-treat, ITT): all randomized participants who were exposed to the study drug, regardless of the degree of protocol compliance during the study. This data set is the main one for the analysis of primary and secondary effectiveness parameters;
2. Population of participants who completed the study according to the protocol (per protocol, PP): all randomized subjects who completed participation in the study in accordance with the protocol (completed the prescribed period of treatment and follow-up without significant deviations from the protocol). This data set is additional for the analysis of primary and secondary effectiveness parameters;
3. Safety population: The data set analyzed for safety assessment is identical to the ITT data set. However, unlike the population depending on the prescribed treatment, participants are analyzed depending on the actual treatment (if it differs from the treatment that was prescribed by randomization). All types of safety analysis will be based on the use of a data set for security assessment;
4. Modified population of all included and randomized participants (intention-to-treat, ITT) not vaccinated against COVID-19: ITT_NV. This data set is additional for the analysis of the primary efficiency parameter;
5. Modified population of participants who completed the study according to the protocol (per protocol, PP), not vaccinated against COVID-19: PP_NV. This data set is additional for the analysis of the primary efficiency parameter;
6. Modified population of all included and randomized participants (intention-to-treat, ITT) not vaccinated against COVID-19 or vaccinated before inclusion in the study: ITT_NV_BE. This data set is additional for the analysis of the primary efficiency parameter;
7. Modified population of participants who completed the study according to the protocol (per protocol, PP), not vaccinated against COVID-19 or vaccinated before inclusion in the study: PP_NV_BE. This data set is additional for the analysis of the primary efficiency parameter.

Thus, the safety population will be used to present demographic data about participants, as well as for safety assessment. ITT will be considered the main sample for comparative analysis of performance parameters. The PP population will include only participants who completed the study without critical deviations from the protocol and will be formed as an additional sample to evaluate the effectiveness parameters in order to analyze the sensitivity of the results obtained in the ITT population. The modified populations will be used to perform sensitivity analysis when evaluating the primary endpoint.

The number of participants who must complete the study in accordance with the protocol is 286 in each group, or a total of 572 participants.

The number of randomized participants is 315 in each group or total of 630 participants.

The number of screened participants is up to 642.

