1. The use of the prohibited therapy indicated above, specific to each of the groups.
2. Withdrawal of informed consent.
3. Compliance to the study therapy is 50% or less.
4. Systematic non-compliance with protocol procedures by the participant.
5. Development of individual intolerance to the study drug (for the study group).
6. The development of concomitant diseases or conditions that, according to the researcher, may distort the results of the study, restrict the rights of the volunteer or put him at greater risk.
7. The appearance of contraindications to the use of the study drug in the period before the last intake of the second 10-day cycle (for the study group).
8. Participation in a clinical trial using a different therapy.
9. Disagreement on following reliable contraceptive measures (sexual abstinence; or a combination of 2 different methods: for example, barrier and spermicides, or barrier and intrauterine device, or barrier and hormonal, etc.) – for participants with preserved childbearing potential in the period before the last intake of the second 10-day cycle (for the study group).
10. Pregnancy.

A woman who excluded from the study due to the onset of pregnancy during the clinical trial is subject to medical supervision during the entire period of pregnancy, as well as for 6 months postpartum period to assess the condition of the woman and the born child (observation is carried out if possible and only if her desire and consent to such observation is mandatory). Information about the course of pregnancy and its outcome is entered in the primary documentation (with the consent of the woman). During the entire period of pregnancy, together with an obstetrician-gynecologist (with the consent of the pregnant woman and, if possible, contact with a doctor), observing a woman, her general condition, data reflecting the nature of the course of pregnancy, results of laboratory and instrumental examination methods, including ultrasound, are analyzed. Monitoring of the born child is carried out with the consent of the woman together with the district pediatrician (if possible, contact with him) until the child is 6 months old to analyze the clinical status of the child, data from laboratory and instrumental research methods.

There are no procedures for replacing excluded participants.

Diaries of participants

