Address of the place of manufacture: [name], J.S.C. "Biomed"-Mechnikov Tel/[contact], [name]

E-mail: [contact] Internet: www.pharmaclon.ru

Labelling: The inscription "For post-marketing research RAIN-2020" is applied to the primary packaging and secondary (consumer) packaging of the study drug product, the inscription "Not for sale" is additionally applied to the secondary (consumer) packaging in accordance with the requirements of the Federal Law "On Circulation of Medicines" dated 12.04.2010 N 61-FZ as amended Federal Law No. 429-FZ from 22.12.2014.

Compliance assessment

Assessment of compliance with study preventive therapy is evaluated on the basis of data recorded in the participant's diary, on visit 3, as well as in advance as part of an oral survey of the participant on a phone call visit after the end of preventive use of the drug. Compliance is assessed on a 100% scale, where:

100% – participant completed 2 cycles of 10-day courses without violating the dosage regimen and the frequency of admission

90% – participant completed 2 cycles of 10-day courses with a single violation of dosage regimen or dosage frequency

80% – participant completed 1 cycle of the 10-day course without violating dosage regimen or dosage frequency

70% – participant completed 2 cycles of 10-day courses with a double violation of dosage regimen or dosage frequency (single violation of each course)

60% – participant completed 1 cycle of 10-day course with a single violation of dosage regimen or dosage frequency

50% or less – participant completed 1 or 2 cycles of 10-day courses with a systematic (twofold or more) violation of the dosage regimen or dosage frequency in each of the courses (non-compliance with a single dose, frequency of use and/or its duration).

Compliance of 50% or less is the criterion for excluding a participant from the study.

STUDY PARAMETERS OF EFFICIENCY AND SAFETY

Effectiveness criteria

Effectiveness criteria will be evaluated according to the data recorded in the participants' diaries, in primary medical documentation.

Primary effectiveness criterion:

The proportion of patients with acute respiratory viral infections, including COVID-19, at the end of the period of preventive administration of the drug (measurement time: 28 days).

Secondary effectiveness criterion:

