- ❖ All participants included in the study (FAS, Full Analysis Set). This population will be used to describe basic characteristics, including demographic and anthropometric indicators, data on concomitant diseases, and will also be used as the main population to assess performance parameters. In this case, the participant's group will be determined by the "intention to treat" (ITT Analysis).
- ❖ Auxiliary analysis of effectiveness parameters is planned for all subjects who completed the study without significant deviations from the study protocol (PP, Per Protocol).

Methods of descriptive statistics

For numerical indicators, such as demographic and anthropometric data (body weight, age, height, BMI), as well as numerical performance parameters will be calculated:

- Number of missing values (N);
- Minimum value (Min);
- Maximum value (Max);
- Arithmetic Mean (M);
- Standard Deviation (SD);
- 95 % confidence interval (CI) for the mean;

- Median (Me).

For qualitative variables (frequency of AE/SAE development, for example), absolute number in the n/N format will be given, as well as the percentage (%).

Analysis of basic characteristics

The distribution of subjects, demographic and baseline characteristics will be presented using descriptive statistics methods for all subjects included in the study (FAS-population). An intergroup comparison of the basic quantitative characteristics will be carried out using the t-test (or the Mann-Whitney test), depending on the type of data distribution. For categorical data, the χ^2 -criterion or Fisher's exact test will be applied if the expected frequency in any of the cells is less than 5.

Standard methods available in the XLSTAT 2020.3 program will be used for data analysis.

When analyzing numerical data, preliminary testing of variables for the normality of the distribution will be carried out using Shapiro-Wilk's test, as well as a test for asymmetry and kurtosis with an indication of the p value when testing the null hypothesis of the normal distribution of the variable. In the case of a normal distribution, an intra-group comparison of parameter changes is carried out using a paired t-test. For a comparative evaluation, the χ^2 -criterion or the exact Fisher test will be used if the expected frequency in any of the cells is less than 5.

Significance level

A significance level of 0.05 will be used in all tests. Correction for the multiplicity of comparison is not introduced.

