2. CLINICAL TRIAL DESIGN

2.1. Design

Post-marketing non-interventional prospective randomized open-label comparative study.

A total of 4 visits are planned (0–3). Visit 0 and 1 can be combined.

During randomization, participants are randomly distributed in a 1:1 ratio into two groups:

[figure not shown]
Group I (main) and Group II (control).

According to the methodology approved by this protocol, the participant must use (Group I) or not use (Group II) study drug (depending on the distributed randomization number at Visit 1) for 27 days of the preventive course (10 days + 7 days + 10 days).

The effectiveness of preventive therapy will be recorded. The presence and severity of any adverse events and events will also be evaluated, regardless of the alleged connection with the use of the study drug Ingaron®.

The schedule of visits and procedures is identical for all study participants. A detailed description of the research procedures is provided in the Protocol.

The schedule of research procedures is presented in the section DESIGN of NON-INTERVENTIONAL RESEARCH Protocol. The study periods with the planned time are shown in the diagram below:

Scheme 1. Design

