Analysis of the source data

Demographic characteristics, baseline, and follow-up characteristics such as anamnesis, comorbidities and medications used will be described by treatment groups for the ITT population and then safety, if they differ.

⁶ URL <https://www.R-project.org/>

⁷ <https://www.r-project.org/doc/R-FDA.pdf>

Primary Endpoint Analysis

The main parameter of the effectiveness of the preventive use of Ingaron® is the proportion of patients with acute respiratory viral infections, including COVID-19, at the end of the period of preventive administration of the drug (measurement time: 28 days).

In accordance with the purpose and objectives of the study, the null and alternative hypotheses are formulated as follows:

- Null hypothesis (H_0) consists in the assumption that the prophylactic administration of Ingaron will not lead to a change in the incidence of acute respiratory viral infections, including COVID-19, among adult volunteers;
- Alternative hypothesis (H_a) is that in the study group, the proportion of ARVI cases, including COVID-19, will differ from the control group.

$$H_0: \mu_1 = \mu_2$$

$$H_a: \mu_1 \neq \mu_2,$$

where μ is the fraction of the main variable for the corresponding group.

To test these hypotheses, the method of a two-way variant of the Fisher's exact test (with expected frequencies less than 5) or the Pearson's chi-squared test (χ^2) (with the Yates correction for expected frequencies more than 5, but less than 10) will be used.

In all cases, the significance level (α is the probability of an error of the first kind) 0.05 will be used.

The analysis of the primary efficiency parameter will be carried out on the ITT population (main analysis), as well as – additionally – on the PP population (additional analysis).

Data on the case of ARVI (COVID-19) is collected during the entire study by filling out a form on the registration of a case of ARVI.

Secondary Endpoint analysis

The following secondary efficacy parameters in this study are quantitative indicators that will be compared between treatment groups:

- proportion of patients with confirmed COVID-19 at the end of the period of preventive administration of the drug (measurement period: 28 days);
- proportion of patients with acute respiratory viral infections, including COVID-19, at the end of the observation period (change period: 2 months);
- percentage of patients with confirmed COVID-19 at the end of the follow-up period (change period: 2 months);

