5.3. Missing / incorrect data

For all parameters, the analysis will be carried out only on the available information, without filling in the data. There are no plans to use data reconstruction methods in this study.

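### The SAP limits its main ITT set to participants exposed to the study drug, which contradicts its own title and the protocol's FAS and which no compliant untreated control can meet

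*SAP*

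**What the plan says.** The title of SAP 5.5 item 1 covers all included and randomised participants. Its definition is narrower: "all randomized participants who were exposed to the study drug, regardless of the degree of protocol compliance during the study". SAP 5.1 and 5.5 make this the main set for the primary and secondary endpoints. The protocol (Populations for analysis) uses a set without that limit, "All participants included in the study (FAS, Full Analysis Set"), with groups taken by intention to treat.

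SAP 2.1 states the allocation: "the participant must use (Group I) or not use (Group II) study drug". The protocol prohibits interferon gamma in the control group (Prohibited therapy), makes prohibited therapy a ground for exclusion (Exclusion criteria, item 1), and offers controls a vial only on completing the study (note 5 to the schedule of procedures). The trial is open-label (SAP 2.3), and Group I instils the drug at home.

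On the safety set, SAP 5.5 item 3 says: "The data set analyzed for safety assessment is identical to the ITT data set". SAP 5.4, which covers departures from the protocol and the original plan, deals only with vaccination-status analyses and does not mention an exposure condition.

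**The concern.** An intention-to-treat set should be fixed by randomisation alone. Here the defining sentence adds a condition that depends on what happened afterwards and that only one arm can meet. Someone must therefore decide what the sentence means, and in an open-label trial that decision could be made with outcomes known.

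If a dose is required in Group I while randomisation is enough in Group II, never-dosed participants leave one arm only. Where they differ in infection risk from those who started, the comparison is no longer between randomised groups. The wording also reaches the safety set, which is tied to ITT, and arguably ITT_NV and ITT_NV_BE, which are described as modifications of it.

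**Working it through.** **1. The passages side by side**

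| Source | Who is in the main set |
|---|---|
| SAP 5.5 item 1, title | All randomised: 315 + 315 = 630 |
| Protocol FAS | All included, by assigned group: 630 |
| SAP 5.5 item 1, definition read literally | At most 315 in Group I, 0 compliant controls |
| Dose required in Group I only | 315 minus the never-dosed, against 315 |

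The literal reading cannot be intended, because the ITT table shells (Tables 8 to 16) report Group II. That leaves the first two rows, which agree, or the last.

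**2. Inputs**

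- Group size: the protocol's formula gives 1.96² × (0.05×0.95 + 0.02×0.98) / 0.03² = 286.4, stated as 286. Then 286 × 1.1 = 314.6, stated as 315.
- Incidence p: 1–5% in controls (protocol, Number of participants).
- Test: two-sided 0.05; Fisher if an expected count is below 5, Yates-corrected chi-squared from 5 to 10, otherwise Pearson (SAP 5.1).
- Assumed, because the documents give neither: non-starter share f in Group I of 2%, 5% or 10% (10% would use up the whole early-exclusion allowance, so it is a generous upper end), and non-starter to starter risk ratio r of 0.5, 1, 2 or 3. No drug effect.

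**3. Bias if only Group I non-starters are dropped**

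Starters' risk = p / (1 − f + f·r). Bias = p minus that; positive favours the drug. Examples at p = 5%:

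- f = 2%, r = 2: 5/1.02 = 4.90, bias +0.10 points
- f = 10%, r = 3: 5/1.20 = 4.17, bias +0.83 points
- f = 10%, r = 0.5: 5/0.95 = 5.26, bias −0.26 points
- r = 1: bias 0 for any f

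**4. Chance of a significant result favouring the drug when it has no effect**

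Exact binomial enumeration at p = 5%, with 315 controls. The r = 1 column is the proper comparator, because it has the same group sizes and no bias.

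| f (Group I n) | r = 0.5 | r = 1 | r = 2 | r = 3 |
|---|---|---|---|---|
| 2% (309) | 2.28% | 2.43% | 2.76% | 3.12% |
| 5% (299) | 2.03% | 2.39% | 3.23% | 4.22% |
| 10% (284) | 1.61% | 2.27% | 4.03% | 6.33% |

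With nobody dropped (315 against 315) the figure is 2.53%. The gap between 2.53% and the r = 1 column comes from sample size and the discreteness of the test, not from bias.

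At p = 3%, r = 2–3 gives a bias of 0.06–0.50 points and a chance of 1.73–3.13%, against 1.57–1.41% at r = 1. At p = 1% the bias is at most 0.17 points, and the chance is at most 1.26%, against 0.69–0.83%.

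**5. Cost of keeping non-starters**

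Take a true 2% in the dosed and 5% in the undosed and the controls. The chance of a significant favourable result, kept against dropped, is 49.7% and 49.2% at f = 2%, 46.9% and 47.5% at 5%, and 42.3% and 45.9% at 10%. The largest loss is 45.9 − 42.3 = 3.6 points. All these figures are well below 80% because the sample-size formula has no power term, which is a separate matter.

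**The case against.** The strongest reply is that the SAP shows what it means. SAP 5.1 describes baseline data for all subjects included in the study and labels them the safety population. Item 3 says of the safety set: "The data set analyzed for safety assessment is identical to the ITT data set". Together these equate ITT with everyone included, in line with item 1's title and the protocol. Table 21 also counts control adverse events from randomisation. Table 20 lists Group I events only after at least one use of the drug, but that limits which events are listed, not who belongs to ITT. Table 1 would show any one-sided loss from ITT. All of this stands: the documents lean towards loose wording and away from a planned one-arm exclusion. It does not remove the clause, and the words after it protect poor compliers who took some drug, not those who took none.

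Three stronger readings are tempting and are not supported:

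- **The SAP plans to analyse no controls.** The Group II columns in the ITT tables rule this out.
- **Other rules also remove never-dosed participants from ITT.** The protocol says: "Compliance of 50% or less is the criterion for excluding a participant from the study". Exclusion from the study is not exclusion from ITT, and item 1 keeps participants whatever their compliance. The available-data rule in SAP 5.3, "For all parameters, the analysis will be carried out only on the available information, without filling in the data", applies to both arms alike.
- **The clause inflates false positives.** That holds only if the one-sided reading is adopted and non-starters are at higher risk. The 6.3% needs 10% non-starters at triple risk. At 3% incidence with up to 5% non-starters the chance never exceeds 2.36%.

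**Conclusion.** The defect in the text is certain and needs no assumption: item 1 contradicts its own title and the protocol FAS, is not declared as a change in SAP 5.4, and sets a condition that compliant controls cannot meet. The intended meaning is probably everyone randomised, but the plan does not say so, and the alternative is a post-randomisation exclusion in one open-label arm.

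The size of the harm is conditional. Under the one-sided reading at 5% incidence it ranges from 0.26 points against the drug to 0.83 points in its favour, is zero at equal risk, and is negligible at 1% incidence. The direction cannot be known in advance. This should be fixed, but it does not show that the primary analysis is biased.

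The mention of PP as the primary-analysis population in the protocol's Number of participants section is a separate point.

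**What to change.** - **ITT.** Delete the exposure clause. Define ITT (FAS) as all randomised participants, analysed in the assigned arm whether or not any drug was taken. Build ITT_NV and ITT_NV_BE from it.
- **Excluded participants.** State that those excluded under the protocol's exclusion criteria, including item 3 ("Compliance to the study therapy is 50% or less"), stay in ITT with the ARVI/COVID-19 status already collected. Report by arm how many lack a Day-28 status: the schedule puts Visit 2 at day 27 ± 3, so a visit on day 24–27 may not supply one, and SAP 5.3 plans no imputation.
- **Safety set.** Define it separately: Group I with at least one instillation plus all randomised Group II, by actual treatment.
- **Baseline tables.** SAP 5.1 says that these characteristics "will be described by treatment groups for the ITT population and then safety, if they differ". An earlier paragraph of 5.1, the closing text of 5.5 and Tables 2–7 put them on the safety population. Reconcile these so that ITT comes first, and safety follows if it differs.
- **Table 1.** Add a row for never-dosed participants.

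The cost is a few sentences and one table row. If Day-28 status is available for non-starters, keeping them costs at most about 4 points of power, at an assumed 10% non-starters. At 2% there is no loss.
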